## **1.0 Objectives**

### **1.1 Study Objectives**

The objective of the study is to evaluate the efficacy and safety of adding transdermal preparation of granisetron (Sancuso ®) to the current postoperative nausea and vomiting (PONV) standard prophylaxis regimen with dexamethasone and diphenhydramine in patients with the previous history of severe, particularly delayed and/or post-discharge, PONV and undergoing surgical procedure under general anesthesia.

The specific aims of the study include:

1. efficacy of the investigated therapy in prevention of PONV up to 120 hours after surgery
2. incidence and seriousness of the observed side effects
3. ability of patients to self-administer preoperatively and maintain the investigated patch during the perioperative period
4. level of satisfaction with the preoperative PONV prophylaxis.

### **1.2 Primary Study Endpoints**

Number of complete responders (CR, defined as no nausea or vomiting/retching episodes during 120 hours postoperatively, no additional antiemetic medication up to 120 hours after surgery)

### **1.3 Secondary Study Endpoints**

Frequency and severity of nausea and vomiting during the observed period, patient satisfaction scores, length of stay, frequency of re-admission, frequency and type of side effects

## **2.0 Background**

### **2.1 Scientific Background and Gaps**

Postoperative nausea and vomiting (PONV) are common and distressing symptoms to patients. The general incidence of vomiting is about 30%, the incidence of nausea is about 50%, and in a subset of high-risk patients, the PONV rate can be as high as 85%. Unresolved PONV may result in prolonged post anesthesia care unit (PACU) stay and unanticipated hospital admission that result in a significant increase in overall health care costs. The goal of PONV prophylaxis is therefore to decrease the incidence of PONV and thus patient-related distress and reduce health care costs. The major shortcoming of currently used antiemetics is their relatively short duration of prophylactic activity (e.g., about 4-6 hours for all 5HT3 receptor antagonists- 5HT3RA)

requiring its repeated dosing or, for longer acting antiemetics (e.g., scopolamine patch or dexamethasone), the presence of significant side effects and limited effectiveness.

It was reported previously that IV granisetron could be more effective than other 5HT3RA antiemetics because of its unique metabolic pathways and stronger 5HT3 receptor affinity. It is therefore important to investigate if the administration of granisetron in the prolonged activity formulation will provide effective antiemetic prophylaxis beyond 24-48 hours after administration.

It is proposed that the non-invasive patch application could extend the available repertoire of the current 5HT3RAs oral or IV regimens in PONV. Sancuso® was approved by the United States (US) Food and Drug Administration (FDA) in September 2008, and is indicated for the prevention of nausea and vomiting in patients receiving moderately and/or highly emetogenic (HE) chemotherapy regimens of up to 5 consecutive days' duration. The present study will evaluate its effectiveness in the prophylaxis of PONV.

## 2.2 Previous Data

Granisetron as the hydrochloride (HCl) salt has been approved as an anti-emetic and marketed since the early 1990s. Prior to its approval, a comprehensive development program was conducted and the data submitted for registration. Currently available granisetron formulations (oral and iv) were first marketed in the early 1990s (trade names include Kytril® and Kevatril®). Generic oral and iv granisetron formulations are now available. In the extensive clinical experience gained since, these formulations have proven highly effective in the prevention of CINV, and no post-marketing safety concerns have arisen. Clinical Studies of Sancuso® in CINV (no published work available about its effects in PONV)

- A Phase I PK study (in 6 male and 6 female healthy subjects) demonstrated the delivery of granisetron over 5 days from a 15 cm^2 TDS applied to the abdomen. Mean maximum observed plasma concentration (Cmax) was approximately 1.9 ng/ml and the approximate plateau value achieved equated to 1.1 ng/ml (392MD/4/C).
- A Phase I relative bioavailability study (in 12 healthy male subjects) of 4-way cross-over design, compared 3 dosages of Sancuso® (15, 33 and 52 cm^2) after a single 6-day application to the upper arm, to that of a 2 mg once-daily oral dose of granisetron for 5 days. Data indicated that average observed plasma concentration (Cavg) was reached after 24 hours and maximal concentrations were reached 48 hours after patch application. Based on Cavg, a 52 cm^2 TDS applied for 6 days resulted in a similar plasma concentration to that obtained with once-daily oral dosing of 2 mg granisetron. The pharmacokinetics of granisetron showed dose-proportionality (392MD/11/C).
- A Phase II study (in 175 patients receiving moderately emetogenic (ME) single-day chemotherapy) evaluated efficacy of Sancuso® for the prevention of acute and delayed CINV. Efficacy of Sancuso® in acute emesis was comparable to the reference product, a single oral dose of 2 mg granisetron; in delayed emesis, efficacy was no different from placebo TDS. Sancuso® was well-tolerated (392MD/8/C).
- A Phase III multi-national study (in 637 patients receiving MEC (moderately emetogenic chemotherapy) and HEC (highly emetogenic chemotherapy) multi-day chemotherapy) evaluated the efficacy, tolerability and safety of Sancuso® in prevention of CINV associated with multi-day chemotherapy. The study demonstrated non-inferiority of Sancuso® to oral granisetron in complete control (CC) of nausea and vomiting over the course of multi-day ME or HE chemotherapy (392MD/15/C and Boccia et al, 2010).
- A study to evaluate the skin irritation and sensitization potential of Sancuso® in 212 healthy subjects assessed the cumulative skin irritation and sensitization potential of Sancuso® over a 21-day period. The study concluded that Sancuso® and its matching placebo are slightly irritant when applied on healthy skin, with a lower

number of subjects reporting irritation with the active Sancuso® patch. A low sensitization potential was detected for the active Sancuso® patch. Plasma concentrations in a subset of 24 subjects were assessed following the first patch application, resulting in the apparent dose of the patch of 3.1 mg/24 hours (392MD/26/C).

- A Phase I study in 12 healthy subjects investigated the pharmacokinetics, safety and tolerability of Sancuso® as add-on therapy to iv granisetron. The results from this study indicate that for multiple-day chemotherapy regimens it is possible to administer a single iv dose of granisetron on Day 1 (the same day that the patch is applied) if the patch is not applied 24-48 hours before the start of chemotherapy, allowing granisetron concentrations to achieve target levels immediately on Day 1 without a subsequent effect on the known PK and safety profile of the Sancuso® patch over the following days (392MD/35/C).
- A Phase I study in 12 healthy subjects evaluated the PK and safety profile of the co-administration of iv granisetron and the Sancuso® patch, and the PK profile of repeat Sancuso® patch application. Following combined iv and transdermal administration of granisetron, the plasma concentration vs time profiles exhibited three peak concentrations which reflected the iv administration, the concurrent transdermal patch application, and the subsequent patch application one week later. Sustained mean concentrations of granisetron were observed over the 0 to 24 hours period (with a mean increase between 12 and 24 hours). Peak plasma concentrations relating to transdermal administration of granisetron were achieved approximately 48 hours after each patch application. There was minimal evidence of accumulation following the second transdermal administration of granisetron. Sancuso® was well tolerated when 2 patches were applied consecutively, each for a period of 7 days. Similarly, Sancuso® raised no safety concerns when co-administered with an iv dose of granisetron (392MD/41/C).
- A Phase I study (conducted by Solasia Pharma K.K., Japan) investigated the pharmacokinetics, safety and tolerability of Sancuso® in 12 healthy male Japanese subjects. The PK profile in healthy male Japanese subjects in this study was similar to that seen in a previous study in healthy male non-Japanese subjects. Changes in the clinical safety assessments were unremarkable and the study drug was well-tolerated in healthy Japanese males (SP-0101).
- A Phase I study investigated the effects of Sancuso® on electrocardiogram (ECG) parameters, safety and tolerability compared to placebo and moxifloxacin (positive control) in 240 healthy adult subjects (120 male and 120 female). No clinically significant effect of Sancuso® on ECG parameters was observed (392MD/39/C).
- A Phase I study evaluated the effect of age (Part I) and body mass index (BMI) (Part II) on the pharmacokinetics, safety and tolerability of Sancuso®, each in 30 healthy adult subjects. Quantifiable granisetron concentrations were recorded between 24 and 168 hours post application of Sancuso®. Median time of the maximum observed plasma concentration ( $t_{max}$ ) values ranged between 60.14 and 72.12 hours across the 5 study groups. No statistically significant differences were reported between the age groups or among the BMI groups for the PK parameters of  $C_{max}$ , area under the plasma concentration-time curve between time 0 and the time of last quantifiable sampling point ( $z$ ) ( $AUC [0-z]$ ), area under the plasma concentration-time curve between time 0 and infinity ( $AUC [0-\infty]$ ) and  $C_{avg}$ . It was determined that the continuous variables age, BMI and age\*BMI (interaction) have no predicting properties for these parameters (392MD/40/C).
- A Phase I study evaluated the effect of heat on the pharmacokinetics, safety and tolerability of Sancuso® in 8 healthy male and 8 healthy female subjects. Heat was applied using a Cura-Heat® Back & Shoulder pad with a measured local temperature of approximately 42°C (107.6°F). No overall effect of heat on the PK of Sancuso®

## 2.3 Study Rationale

Clinical guidelines recommend the use of 5HT3RAs in the prevention of PONV and chemotherapy-induced nausea and vomiting (CINV). Granisetron is a potent 5HT3RA, with little or no affinity for other serotonin receptors, or for dopamine-D2, histamine-H1, benzodiazepine and opioid receptors.

Oral and intravenous (iv) formulations of granisetron have been marketed for over 15 years. They are licensed for the prevention of PONV and nausea and vomiting associated with initial and repeat courses of emetogenic cancer therapy, including high-dose cisplatin, which has a strong emetic effect in more than 90% of patients.

ProStrakan, Limited has developed a new granisetron formulation, Sancuso® , a transdermal delivery system (TDS) (granisetron TDS or patch) for the prevention of CINV. Sancuso® consists of a stable matrix of granisetron base (6% w/w) in a commercially-available adhesive (DURO-TAK ® 387-2287), designed to sustain delivery of granisetron over a number of days following topical application. Pharmacokinetic evaluation of Sancuso ® has indicated that it provides continuous delivery of granisetron over 7 days, providing exposure similar to an oral dose of 2 mg per day (Howell et al, 2009). Previous data indicate prolonged activity of this preparation in prophylaxis of CINV. There is no data available about the efficacy of this formulation in the prophylaxis of PONV.

It should be noted however that there is increasing concern among anesthesiologists and surgeons about patients displaying so called post-discharge (or late) form of PONV. These symptoms occur at least 48-72 hours after the procedure and may last several days (often after patient has been already discharged from the medical facility). It is therefore feasible that the investigated formulation of granisetron will provide prophylactic antiemetic activity throughout the entire period, including acute and delayed phases of PONV.

## 3.0 Inclusion and Exclusion Criteria

### 3.1 Inclusion Criteria

- Patients that are between the ages of 18 and 89
- Scheduled to undergo surgical procedures with general anesthesia
- Seen in the anesthesia clinic at least 24 hours before surgery
- History of severe PONV after previous general anesthesia
- Surgical procedures with anticipated duration > 1 hour and no more than 5 hours
- American Society of Anesthesiologists (ASA) physical status I to III

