### **7.2 Study Procedures**

Patients will be recruited from the surgical population undergoing preoperative evaluation in Anesthesiology Preoperative Evaluation Clinic at Hershey Med. Ctr. (~15,000 per year). Selected patients (ASA 1-3, N=60) with history of severe PONV after one or more of previous general anesthesia, and scheduled to undergo surgical procedures with general anesthesia will be enrolled into IRB approved protocol. The patch will be placed by the patient at home 24 – 48 hours before surgery as directed by the doctor. The subsequent standardized general anesthesia protocol for elective surgery will include general endotracheal anesthesia with sevofluran, including standard intraoperative PONV prophylaxis (IV dexamethasone and 4 mg and diphenhydramine 25 mg ). Postoperative evaluation will include recording of incidence and severity of PONV at the time of discharge from PACU (acute PONV), and at 120 hrs (delayed or post discharge PONV). The final phone interview will be performed 7 days after patch removal in order to capture possible side effects after discontinuation of medication.

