#### **7.2.1 Visit 1 - Anesthesia Preoperative Evaluation Clinic and recruitment and drug dispensation**

Patient is seen in clinic and identified as having a history of serious PONV, in particular delayed or post discharge PONV. Study will be explained to the patient and consent obtained. The investigational pharmacy will be notified that a study patient has been enrolled and they will prepare the patches for distribution to the patient. EKG will be performed and the results will be recorded preoperatively.

A member of the research team will obtain the assigned patches from the investigational pharmacy and deliver to the anesthesia provider (member of the research team).

The provider will then demonstrate to the patient how to apply the patch and the patient can practice using a placebo patch to show that the correct placement. Patient will then take the actual patch home with them. Patient will also be given a PONV diary to take home with them. Upon returning home from surgery, the patient will be asked to record their instances of nausea and vomiting on a daily basis for up to five days after surgery. At hour 120 post-op, a case manager will telephone the patient and note any recorded

instances of nausea and vomiting since the patient has returned home. The case manager will also check the status of the patch and any medications that were taken as a result of nausea and vomiting. One week after removal of patch (120h post-op + 7 days), a case manager will call the patient a final time to collect adverse events and to assess patient satisfaction with the patch.

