#### **7.2.2 Visit 2 - approximately 24-48 hours preoperatively (patient's home)**

Patient will apply the patch to their upper arm 24-48 hours before scheduled surgical procedure, as instructed during their pre-op anesthesia visit. The patch will then remain in place until 120 hours after surgical procedure. No backup patch will be provided so the patients with the accidentally missing patch will need to call their primary surgical service for the standard antiemetic medication.

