###### **7.4.6.3 Preparation and Dispensing**

Upon enrollment, the PI will write a prescription for the patch and that will be faxed to the pharmacy. The pharmacy will assign a patch to the patient and a member of the research team will pick that up from the pharmacy and deliver it to the anesthesiologist (research team member). The provider will then educate the patient on how to apply the patch to the upper arm

area. The patient will have the opportunity to practice applying the patch using a placebo patch (supplied by the sponsor). The patient will then take the patch home and apply at minimum 24 – 48 hours before surgery as hours (no longer than 48 hours) before surgery.

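### The minimum clinic-visit lead time equals the minimum patch-application lead time, so patients seen about 24 hours before surgery are eligible but cannot apply the patch within the window

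*Combined protocol and SAP*

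**What the plan says.** All references are to the combined protocol and SAP.

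- **Eligibility (3.1).** The only timing condition on the clinic visit is "Seen in the anesthesia clinic at least 24 hours before surgery".
- **What happens at the visit (5.1.1.1, 7.2.1, 7.4.6.3).** Consent follows the preoperative evaluation. An ECG is done and the investigational pharmacy is notified. A prescription is faxed once the patient is enrolled, the pharmacy assigns a patch, and a team member collects it. The provider teaches application and the patient may practise with a placebo patch. Then: "Patient will then take the actual patch home with them".
- **Application.** Section 7.2: "The patch will be placed by the patient at home 24 – 48 hours before surgery as directed by the doctor". Section 7.2.2: "Patient will apply the patch to their upper arm 24-48 hours before scheduled surgical procedure". The heading of 7.2.2 is looser: "approximately 24-48 hours preoperatively (patient's home". Section 7.4.6.3 begins "The patient will then take the patch home and apply at minimum 24" and continues to 48 hours in a sentence that is garbled, but that also names 48 hours as the longest interval.
- **Check on the day of surgery (7.2.3).** The team records when the patch was applied and whether it is correctly placed and intact. Nothing is said about an application time outside the window. The removal criteria (3.3.1), the compliance section (7.4.4) and the statistical methods (9.2) do not mention one either.
- **Pharmacokinetics (2.2).** In one study the average concentration "was reached after 24 hours and maximal concentrations were reached 48 hours after patch application". In the age and BMI study, "Quantifiable granisetron concentrations were recorded between 24 and 168 hours post application", with median times to peak of 60.14 to 72.12 hours.

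**The concern.** A visit 24 hours before surgery satisfies 3.1. The patch can go on only after everything listed for that visit and the journey home, so it goes on less than 24 hours before surgery. The protocol therefore enrols patients for whom its own application window is out of reach, and it does not say how their data are to be read.

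The primary endpoint gives this some weight. Complete response (1.2, 7.2.3) covers the whole 120 hours after surgery, so one episode or one rescue dose in the PACU makes the patient a failure for the full period, whatever happens later. If a shorter patch lead time has any effect on early symptoms, that effect enters the primary result and cannot be separated from failure of the product under its intended schedule. With 60 evaluable patients (16.0), each such failure moves the rate by 1/60 = 1.7 percentage points.

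**Working it through.** The plan states no figure that depends on this timing, so there is none to reproduce. The check is arithmetic on the stated limits.

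**Inputs**
- L, clinic visit to surgery: at least 24 h (3.1).
- Required patch lead time: 24 to 48 h (7.2, 7.2.2, 7.4.6.3).
- d, clinic visit to home application: not given. Assumed range 1 to 6 h.
- s, anticipated duration of surgery: more than 1 h and up to 5 h (3.1).

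**Step 1: patch lead time.** Longest achievable lead = L − d. For a patient seen at L = 24 h:

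| d (h) | Lead = 24 − d (h) | Meets 24 h? |
|---|---|---|
| 1 | 23 | no |
| 2 | 22 | no |
| 4 | 20 | no |
| 6 | 18 | no |

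The conclusion does not depend on the assumed range: any d above zero gives a lead below 24 h.

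**Step 2: which visits are affected.** The window is missed whenever L < 24 + d. The affected band runs from 24 h to 25 h (d = 1), 26 h (d = 2), 28 h (d = 4) or 30 h (d = 6). A patient seen 26 h ahead complies if d is 2 h or less, but not if d is 4 h. The documents do not give the distribution of clinic-to-surgery intervals, so the share of patients in this band cannot be computed.

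**Step 3: how much early exposure is lost.** The 120-hour period starts at the end of surgery. Patch wear at that moment = (L − d) + s. With s taken from 1 to 5 h:

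| Patient | Wear at end of surgery (h) |
|---|---|
| Applies exactly 24 h ahead (within the window) | 25-29 |
| Seen at 24 h, d = 1 | 24-28 |
| Seen at 24 h, d = 2 | 23-27 |
| Seen at 24 h, d = 4 | 21-25 |
| Seen at 24 h, d = 6 | 19-23 |

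Acute PONV is recorded at PACU discharge, so PACU time is added to every row. Compared with the latest application the window allows, the shortfall is d itself, 1 to 6 h. At the end of surgery these patients are close to, and in part past, the 24 h after which section 2.2 reports that the average concentration was reached.

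**Step 4: direction.** Complete response includes the acute phase. Less early drug could only add early failures, so any effect would lower the response rate and work against the patch in the comparison with the historical failure rate (9.1).

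**The case against.** The case for treating this as minor has several parts.

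*The window may not be strict.* The heading of 7.2.2 is approximate and the sentence in 7.4.6.3 is garbled. That stands as far as it goes, but no tolerance is defined. The text of 7.2 and 7.2.2 gives the interval without qualification.

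*A reader might infer that late-seen patients go through the acute phase with little drug on board.* The documents do not support that. They give no concentration for the patch alone before 24 h and no target level for PONV. The report of quantifiable levels between 24 and 168 h comes without a sampling schedule and does not say that earlier levels were unquantifiable. Surgery and PACU time bring these patients to about 19-28 h of wear or more at the acute assessment. The late peak (48 h in one study, about 60-72 h in another) also applies to a patient who applies at 24 h and complies fully, so it belongs to the window itself and not to the eligibility line.

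*A reader might also infer that a late application counts as a patient failure under the third specific aim.* Section 1.1 speaks of self-administering before surgery and maintaining the patch. It does not require a set time, and no section scores timing. A patch applied 20 h ahead still satisfies that wording.

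*The effect may be small.* This is an open-label single-arm pilot with particular interest in delayed and post-discharge symptoms, where a few hours matter least, and any bias is against the product. This stands, and it limits the size of the point. It does not remove the mismatch between the sections or supply the missing rule for late applications.

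**Conclusion.** The scheduling conflict is real and follows from the protocol's own text. Section 3.1 and the application sections share a 24-hour minimum although one step must come after the other, and no section says how an application outside the window is handled. With an assumed delay of 1-6 h, a patient seen at exactly 24 h applies the patch 18-23 h before surgery, and visits between 24 h and about 25-30 h ahead are affected.

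The consequence is modest: early exposure 1-6 h shorter than the shortest the window allows, with a possible lowering of the complete response rate. Its size cannot be calculated, because neither the share of affected visits nor the effect of a few hours' lead time on acute PONV is given. It is probably small. The existence of the conflict requires only that the delay be greater than zero; the hour figures rest on the assumed delay.

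**What to change.** 1. Reconcile 3.1 with 7.2, 7.2.2 (text and heading) and 7.4.6.3, so that the minimum interval from clinic visit to surgery exceeds the minimum application interval by at least the time needed for dispensing, training and travel. Which application interval to keep is for the investigators to decide. State it once, in the same terms throughout, with any tolerance defined.
2. State in 9.2 how patients whose application falls outside the window are handled in the primary analysis.
3. Use the application time already recorded on the day of surgery. Tabulate out-of-window applications separately and describe acute response by actual patch-to-surgery interval. With 60 patients and a possibly very small out-of-window group, this table is descriptive and should carry no test.

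The cost is one eligibility line, one sentence in the analysis section and one table from data already collected. The downside is that some patients seen the day before surgery become ineligible. Their number is not given, but it is likely to be few for a study of 60 drawn from a clinic that sees about 15,000 patients a year.
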